1.1.2. Study Objectives

The following objectives are defined in the Study Protocol (Amendment 9, 09 February 2017). The response criteria referenced throughout the Study Objectives are provided in [Section 8](#).

Primary objectives for Stages 1, 2, 3, and 4 are as follows:

Stage 1: The objectives of Stage 1 are to:

- Determine the maximum tolerated dose (MTD), or the maximum tested dose where multiple dose limiting toxicities (DLTs) are not observed, of tagraxofusp.

Stage 2: The objectives of Stage 2 are to:

- Determine the efficacy of tagraxofusp in patients with BPDCN, as assessed by objective response rate (ORR).
- Characterize the safety profile of tagraxofusp at the MTD or maximum tested dose in both patients with AML and BPDCN.

Stage 3: The objectives of Stage 3 are:

- Determine the complete response (CR) rate (ie, CR + CR with incomplete blood count recovery [CRI] + CR [clinical] with minimal residual skin abnormality [CRC]) in patients with first-line BPDCN. Note that these objectives are supported by prespecified statistical hypotheses and were evaluated using appropriate statistical inference during the initial reporting of this study.
- Characterize the safety profile of tagraxofusp in patients with first-line BPDCN.

Stage 4: The objectives of Stage 4 are to:

- Further characterize the efficacy of tagraxofusp in first-line and R/R patients with BPDCN following the completion of Stage 2 and Stage 3 as assessed by the rate of CR (CR + CRI + CRC).
- Further characterize the safety profile of tagraxofusp among first-line and R/R patients with BPDCN.
- Characterize the efficacy and safety of a lyophilized formulation of tagraxofusp among first-line and R/R patients with BPDCN.

Secondary objectives include:

- Determine the CR rate (CR + CRI + CRC) for Stage 1 and 2 patients, and ORR for Stage 3 patients.

- Estimate duration of response (DOR), progression-free survival (PFS) and overall survival (OS) in patients with BPDCN. Note that for patients that received a stem cell transplant (SCT), duration of response includes time pre- and post-SCT.
- Enable preliminary characterization of the estimated ORR in patients with R/R AML, including subsets of patients with R/R AML categorized by pre-treatment blast counts, cytogenetics, or CD123 measurement.
- Estimate DOR, PFS, and OS in patients with AML.
- Characterize the pharmacokinetics (PK) and immunogenicity of tagraxofusp.

Exploratory objectives are to characterize expression of IL-3R (and other potentially relevant stem cell and disease markers) on leukemia cells in peripheral blood and BM, to evaluate potential changes in IL-3R (and other potentially relevant markers) expression on populations over time, and preliminary correlation of baseline IL-3R (and other potentially relevant markers) expression and clinical efficacy (including response rates).

1.1.3. Study Objectives and Definitions Updates

[REDACTED]

An analysis of Stage 1 and Stage 2 first-line BPDCN patients was performed to assess the relative clinical benefit of the response designations of CR, CRc, and CRI, with benefit defined as duration of response, as defined in [Section 4.3.2](#). Durations of response for patients with best responses of CRc and CRI were compared to duration of response for patients with best response of CR to assess the likelihood that the durations of CR and CRc or CR and CRI would have been derived from the same probability distribution. From this analysis, it was determined that the achievement of CRc corresponded to a durability of response that is very similar to the durability of CR. Patients who attain a response of CRc would be expected to benefit from SL-401 treatment in a similar manner as those patients who achieve CR, thereby justifying the inclusion of the category of CRc in the primary efficacy analysis of Stage 3. The results of the analysis of comparability of CR and CRI did not provide sufficient evidence of similarity.

[REDACTED]

[REDACTED] As a result, the definition of CR has been revised to include both results from patients who achieved either CR or CRc .

In addition to bone marrow clearance and amelioration of other components of disease, the skin component of clinical complete response was defined in the protocol to consist of marked clearance of all skin lesions from baseline, including only residual hyperpigmentation or abnormality with BPDCN identified on biopsy (or no biopsy performed).

[REDACTED]

[REDACTED] for more specificity in the concept of marked reduction of skin abnormality in the context of CRc, and to be consistent with the operational characteristics for this designation used by the study investigators, marked reduction in skin manifestation for a response of CRc was defined as at least a 75% reduction in the mSWAT score from baseline. Further, residual disease was defined as a remaining skin abnormality of 10% mSWAT or less, with this residual

consisting of skin hyperpigmentation or other visual abnormality that was not considered by the investigator to be active disease. (Section 8.2)

1.1.4. Purpose of this Document

This statistical analysis plan (SAP) is designed to outline the methods to be used in the analysis of study data to answer the study objectives related to Stage 4 and provide additional safety summaries related to all enrolled patients. Populations for analysis, data handling rules, statistical methods, and formats for data presentation are provided. The statistical analyses and summary tabulations described in this SAP will provide the basis for the results sections of an updated clinical study report (CSR) for this trial, inclusive of Stage 4 results.

This SAP will also outline any differences in the currently planned analytical objectives relative to those planned in the study protocol.

1.2. Study Design

1.2.1. Synopsis of Study Design

This study is a non-randomized, open-label, multicenter study divided into 4 stages: dose escalation (Stage 1), expansion (Stage 2), pivotal (Stage 3), and supportive efficacy and safety (Stage 4). The targeted patient populations are patients with:

- First-line BPDCN for primary efficacy and safety profile of tagraxofusp (Stages 1 to 4).
- R/R BPDCN for supportive efficacy and supportive safety profile of tagraxofusp (Stages 1, 2 and 4).
- R/R AML and high-risk first-line AML for supportive efficacy and supportive safety profile of tagraxofusp (Stages 1 and 2).

A cycle of therapy consists of administration of tagraxofusp at the identified dose for 5 consecutive days every 21 days (with the entire cycle duration lasting 21 days). tagraxofusp is supplied as tagraxofusp Injection frozen solution (1 mg/mL) for Stages 1, 2, and 3. A lyophilized formulation of tagraxofusp (for Injection, lyophilized powder, for solution; 1 mg/mL) was supplied for dosing in selected patients with AML in Stage 2 and for BPDCN patients enrolled in Stage 4 after 17 March 2017.

Stage 4 is planned to continue enrollment of first-line and R/R BPDCN patients to further characterize the efficacy and safety of tagraxofusp and to evaluate the lyophilized formulation in a subset of patients. Pooled analysis of Stage 4 data with other stages will be performed at the time of the primary analysis of study results.

1.2.2. Randomization Methodology

As this is a single-agent study, randomization is not applicable.

1.2.3. Stopping Rules and Unblinding

Tagraxofusp treatment could be discontinued for any of the following reasons:

- Patient withdrawal of consent

- Occurrence of unacceptable toxicity, including DLT in Stage 1
- Tagraxofusp related anaphylaxis or Grade ≥ 3 hypersensitivity reaction
- Requirement for >1 dose reduction unless there is evidence of AML/BPDCN response (beyond Cycle 1), in which case additional dose reductions are permitted, however these reductions must be discussed with the Medical Monitor and documented in the context of ongoing AML/BPDCN response
- Disease recurrence/progression
- Intercurrent illness that prevents further administration of tagraxofusp
- Patient non-compliance
- Occurrence of pregnancy
- Investigator's decision

The reason for tagraxofusp discontinuation and the date of discontinuation are recorded in the electronic case report form (eCRF).

1.2.4. Study Procedures

The schedules of assessments, as outlined in the study protocol, are provided in [Section 7, Table 7-1](#), [Table 7-2](#), [Table 7-3](#), and [Table 7-4](#).

1.2.5. Efficacy, Pharmacokinetic, and Safety Parameters

1.2.5.1. Efficacy Parameters

The primary evidence of efficacy was derived from an analysis of the rate of CR (CR + CRc), accompanied by an evaluation of the durability of response (including time pre- and post-SCT, for those patients who received SCT), as key secondary endpoints.

[figure not shown]
These analyses will be performed on data BPDCN patients treated at the 12 $\mu\text{g}/\text{kg}/\text{day}$ dose level:

1. Bone marrow CR (BMCR; refer to [Section 4.3.1](#)) and duration of BMCR
2. CR (CR + CRc) rate and duration of CR
4. ORR (CR + CRc + CRi + partial response [PR]) and duration of objective response
6. Proportion of patients who receive an SCT
7. PFS
8. OS

Additional exploratory efficacy analyses will be performed on the above endpoints on pooled data across Stages and on additional exploratory efficacy parameters. Exploratory efficacy parameters will include time to CR (CR + CRc) (TTCR) and time to response (CR + CRc + CRi)

+ PR) (TTR), time to BMCR, time to progression, and relapse-free survival (RFS). In addition, an exploratory efficacy analysis will be performed to assess the rate and duration of CR + CRc + CRI.

Bone marrow response will be assessed using International Working Group (IWG) criteria for AML (for patients with AML or BPDCN) (Cheson, et al. 2003), skin-related response using a weighted BSA/modified Severity Weighted Assessment tool (mSWAT) score (for patients with BPDCN) (Olsen, et al. 2011), and lymph node and visceral response using a modified version of the Revised Response Criteria for Malignant Lymphoma (for patients with BPDCN) (Cheson, et al. 2007). For the patients with BPDCN, assessment of response and disease progression will include evaluation of all sites of disease involvement at baseline, which may include BM, skin, peripheral blood, lymph nodes, spleen, and liver. Response criteria for AML and BPDCN are summarized in Sections 16.1 and 16.2 of the study protocol, Amendment 9. As applicable, up to 6 of the largest dominant nodes or nodal masses should be identified as index lesions for radiographic response assessments. Further detail on the definitions and analysis methods for efficacy endpoints are provided in [Section 4.3](#).

1.2.5.2. Safety Parameters

Safety evaluations performed during the study included physical examinations, Eastern Cooperative Oncology Group (ECOG) performance status, measurement of vital signs, 12-lead electrocardiograms (ECGs), clinical laboratory evaluations (hematology, serum chemistry, coagulation, and urinalysis), and monitoring of adverse events (AEs) (including treatment discontinuation due to AEs), DLTs, and concomitant medications.

Further details on the definitions and analysis methods for safety endpoints are provided in [Section 4.3.6](#).

1.2.5.3. Pharmacokinetic and Immunogenicity Parameters

Summary of noncompartmental PK parameters and PK exposure response to treatment summaries will be described in a separate Modeling and Simulation Plan.

Summary of immunogenicity parameters, including anti-drug antibodies (further characterized for specificity to DT and/or human interleukin-3 [hIL-3]), specific anti-hIL-3 antibodies, and tagraxofusp neutralizing antibodies will be performed.

Further details on these analyses are provided in [Section 4.5](#).

2. PATIENT POPULATION

2.1. Population Definitions

The following patient populations will be evaluated and used for presentation and analysis of the data:

- Modified Intent-to-Treat (mITT) Population: All patients who are eligible based on the screening criteria and who received at least 1 dose of tagraxofusp. For BPDCN patients to be eligible for mITT they must also have diagnosis of disease based on central pathology review to be “Confirmed” or “Inconclusive: Likely BPDCN”. Patients who meet the criteria for mITT will be considered “evaluable.” Patients will be grouped according to the planned dose level at time of enrollment.
- Immunogenicity Population: All patients enrolled in the study who received at least 1 dose of tagraxofusp and had sufficient samples to permit immunogenicity analysis.
- Safety Population: All patients enrolled in the study who received at least 1 dose of tagraxofusp. Patients will be grouped according to the actual dose level received.

The mITT population is the primary population for the analysis of efficacy parameters. The Immunogenicity population will be used for summary of immunogenicity results. Supportive subgroup efficacy analyses will be performed in the mITT population, as described in [Section 3.9](#). When the subgroup is defined by immunogenicity parameters, the population will be mITT patients with sufficient samples collected to permit the respective analysis. The Safety population is the primary population for the analysis of safety.

2.2. Protocol Violations

At the discretion of the Sponsor, major protocol violations, as determined by a review of the data prior to database lock and the conduct of statistical analyses described by this document (including Stage 3 efficacy analysis). The Sponsor or designee will be responsible for producing the final protocol violations file (formatted as a Microsoft Excel file), in collaboration with Veristat and the data monitoring group as applicable. This file will be finalized prior to database lock.

All protocol violations will be presented in a data listing.

3. GENERAL STATISTICAL METHODS

3.1. Sample Size Justification

The sample size was originally planned to be approximately 40-50 patients with BPDCN, including approximately 40 previously untreated patients planned to be treated with the tagraxofusp dose as determined in the completed Stage 1 of this study (12 µg/kg/day). In addition, up to approximately 36 patients with R/R AML were planned to be enrolled in Stage 2 of the study. These sample sizes were not based on a formal statistical approach but were considered reasonable to accomplish study objectives for these phases of the trial.

In Stage 3, a sufficient number of patients were enrolled to ensure 10 evaluable patients would be included, with evaluable patients in the mITT population, defined as patients with a diagnosis

of BPDCN, as confirmed via central pathology review, and who received at least 1 dose of tagraxofusp. [REDACTED]

[REDACTED] The primary efficacy analysis for Stage 3 compared the lower bound of a 2-sided 95% Clopper Exact confidence interval (CI) on the observed CR rate to a clinically meaningless value of 10%. Assuming a CR rate of at least 60%, a minimal sample size of 10 first-line BPDCN patients provided at least 90% power for the primary efficacy assessment. Due to the criteria for evaluability in the BPDCN mITT population requiring central pathology review, 13 first-line BPDCN patients were enrolled in Stage 3 between October 26, 2016 and March 17, 2017. Statistical significance was determined when the lower bound of this CI fell above the rate of 10%.

After completion of enrollment of patients with first-line BPDCN in Stage 3, 39 first-line BPDCN patients were enrolled in Stage 4 (37 treated with study drug and 2 screen failures) and 5 R/R BPDCN enrolled in this study after 29 August, 2016 were enrolled in Stage 4.

3.2. General Methods

All data listings that report an evaluation date will include a relative study day (Rel Day). Pre-treatment and on-treatment study days are numbered relative to the day of the first dose of study drug which is designated as Day 1. The preceding day is Day -1, the day before that is Day -2, etc. The last day of study drug is designated with an "L" (eg, Day 26L). Post-treatment study days are numbered relative to the last dose and are designated as Day 1P, Day 2P, etc.

All output will be incorporated into Microsoft Word files, sorted and labeled according to the International Council for Harmonisation (ICH) recommendations, and formatted to the appropriate page size(s).

Tabulations will be produced for appropriate demographic, baseline, efficacy, safety and immunogenicity parameters. For categorical variables, summary tabulations of the number and percentage of patients within each category (with a category for missing data) of the parameter will be presented. Two-sided 95% CIs will be computed using the Clopper Exact method. For continuous variables, the number of patients, mean, median, standard deviation (SD), minimum, and maximum values will be presented. Time-to-event data will be summarized using Kaplan-Meier methodology using 25th, 50th (median), and 75th percentiles with associated 2-sided 95% CIs, as well as percentage of censored observations. Formal statistical hypothesis testing will be performed on the primary efficacy endpoint, CR (CR + CRc) rate among all evaluable first-line BPDCN patients enrolled in Stage 3, with the hypothesis test performed by comparing the lower-bound of a 2-sided 95% Clopper Exact CI to the benchmark of 10%.

3.3. Computing Environment

All descriptive statistical analyses will be performed using SAS statistical software Version 9.3, unless otherwise noted. Medical history and AEs will be coded using the Medical Dictionary for Regulatory Activities (MedDRA) Version 19.0. Concomitant medications will be coded using the World Health Organization (WHO) Drug Dictionary (September, 2016).

3.4. Baseline Definitions

For all analyses, baseline will be defined as the most recent measurement prior to the first administration of study drug.

3.5. Methods of Pooling Data

Summaries will be displayed by stage of enrollment and drug formulation for FL BPDCN patients treated at 12 µg/kg, for R/R BPDCN at 12 µg/kg and overall, and AML patient groups.

Efficacy analyses for patients with first-line and R/R BPDCN who received 12 µg/kg will be conducted for the patient pools described in [Table 3-1](#).

Table 3-1: Planned Pooling of Data for Efficacy Analysis at 12 µg/kg/day

Disease and Line of Therapy	FL BPDCN				R/R BPDCN		
Patient Population	mITT				mITT		
Stages Included	1&2	3	4	3&4*	1&2	4	1,2 &4
CR + Duration	X	X	X	X	X	X	X
BMCR + Duration		X	X	X			
ORR + Duration	X	X	X	X	X	X	X
Percent SCT		X	X	X			X
PFS		X	X	X			X
OS		X	X	X			X
TTCR		X	X	X			
TTR		X	X	X			
TT BMCR		X	X	X			
RFS		X	X	X			
TTP		X	X	X			

Abbreviations: mITT = modified intent to treat population; PP = per protocol population; BPDCN = blastic plasmacytoid dendritic cell neoplasm; FL = first-line; R/R = relapsed/refractory; CR = complete response (CR + CRc); BMCR = bone marrow complete response; ORR = objective response rate; SCT = stem cell transplant; PFS = progression free survival; OS = overall survival; TT CR = time to complete response (CR + CRi + CRc); TTR = time to response (CR + CRi + CRc + PR); TT BMCR = time to bone marrow complete response; RFS = relapse free survival; TTP = time to progression..

[^] Per protocol analyses to be performed if protocol violations lead to multiple patients being excluded from the Stage 3 PP population.

* Stages 3&4 may be pooled if the distributions are determined to be similar, as described in [Section 3.5.1](#).

3.5.1. Pooling of Stages 3 and 4

Patients with first-line BPDCN in Stages 3 and 4 may be pooled for analysis if the relative distributions of CR and duration of CR are determined to be similar to one another and could arise from the same underlying distribution. The importance of this determination is to support the potential similarities between the frozen liquid formulation and the lyophilized formulation of tagraxofusp. If similarities are observed between the stages, pooling will provide increased sample size and therefore increased precision of estimates.

The assessments for similarity between the Stage 3 and Stage 4 results will proceed as follows:

- 1) Comparison of 90% confidence intervals surrounding CR rate, ORR rate, and percent SCT to determine similarities of coverage
- 2) Permutation test assessing whether the observed percentage difference in CR rate between Stage 3 and Stage 4 could occur by chance or if it is indicative of different distributions
- 3) Permutation test assessing whether the observed differences in duration of CR in Stages 3 and 4 could occur by chance or if it is indicative of different distributions

For the permutation tests, the null hypothesis is that Stages 3 and 4 results arise from the same distributions. For each respective parameter, 10,000 replicate datasets (including all observations from Stages 3 and 4 first-line BPDCN) will be drawn without replacement and summary statistics will be computed to develop the empirical null distribution of possible results. The observed result from Stage 3 and Stage 4 will be compared to the empirical null distribution. If the observed result falls within the 10th to 90th percentiles, it would be considered reasonable that Stages 3 and 4 arose from the same underlying distribution and therefore the pooling of the study results are appropriate.

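### SAP 3.5.1 takes a non-rejected permutation test on about 13 versus 37 patients, with no margin, as support for frozen/lyophilized similarity; a true 20-point CR loss passes the CR check 34% to 61% of the time, depending on an unstated tie rule

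*SAP*

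**What the plan says.** SAP 3.5.1 lets first-line Stages 3 and 4 be pooled if CR rate and duration of CR look alike. It gives the reason: "The importance of this determination is to support the potential similarities between the frozen liquid formulation and the lyophilized formulation of tagraxofusp". For first-line patients, stage and formulation coincide. SAP 1.2.1 states that the drug "is supplied as tagraxofusp Injection frozen solution (1 mg/mL) for Stages 1, 2, and 3", and that Stage 4 BPDCN patients enrolled after 17 March 2017 received the lyophilized product. First-line enrollment in Stage 4 began only after that date (SAP 1.1).

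Three assessments are listed:

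- The first is "Comparison of 90% confidence intervals surrounding CR rate, ORR rate, and percent SCT to determine similarities of coverage". No numerical criterion is attached.
- The second is a permutation test on the difference in CR rate.
- The third is a permutation test on duration of CR. Its statistic is not named.

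For the tests, the null is a common distribution and "10,000 replicate datasets (including all observations from Stages 3 and 4 first-line BPDCN) will be drawn without replacement". The decision rule is: "If the observed result falls within the 10th to 90th percentiles, it would be considered reasonable that Stages 3 and 4 arose" from one underlying distribution, and pooling is then called appropriate.

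The SAP gives no equivalence or non-inferiority margin, no operating characteristics, no treatment of ties and no rule for combining the three assessments.

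**The concern.** The null is equality, and failing to reject it is read as support for equality. Such a rule informs about similarity only if it would usually reject when a difference that matters is present. With about 13 patients on one side that is doubtful. The percentile limits also fall on a coarse discrete distribution, so an unstated tie convention can change the answer.

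Characterizing the lyophilized product is one of the primary objectives of Stage 4, and the SAP still calls that product experimental (SAP 1.1.1). At stake are a similarity statement the data cannot carry and a pooled CR rate whose confidence interval ignores the test that allowed the pooling. The stages are also sequential and non-randomized, and SAP 3.6 plans no covariate adjustment, so stage and formulation effects cannot be separated whatever the test shows.

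**Working it through.** **Inputs from the documents.** Stage 3: "13 first-line BPDCN patients were enrolled in Stage 3 between October 26, 2016 and March 17, 2017". Stage 4: "39 first-line BPDCN patients were enrolled in Stage 4 (37 treated with study drug and 2 screen failures". I use 13 and 37. The analysis set is mITT, whose sizes are not given and may be smaller. SAP 3.1 supplies the planning CR rate of 60%. Protocol 3.7.2 gives 16 evaluable first-line patients at 12 µg/kg/day at the interim.

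**Assumption.** A true CR rate 20 points lower in Stage 4. The documents name no margin, so I vary the reference rate from 60% to 80%.

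**The plan's own figure.** No operating characteristic is stated for the pooling rule. The related Stage 3 power claim (at least 90% with n = 10, 60% against 10%) reproduces. The exact lower 95% bound is 6.7% for 3/10 and 12.2% for 4/10, so success needs 4 or more. P(X ≥ 4 | n = 10, p = 0.6) = 94.5%, and the one-sided error at p = 0.1 is 1.3%.

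**CR check, exact.** Let X ~ Bin(13, p3), Y ~ Bin(37, p4) and T = X + Y. Given T, the permutation null for X is hypergeometric (50 patients, T responders, 13 drawn), with distribution function F. With T fixed, the rate difference increases with X, so its percentile is that of X. There are three readings of the rule:

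- inclusive: F(x) ≥ 0.10 and F(x−1) < 0.90
- mid-percentile: 0.10 ≤ [F(x−1) + F(x)]/2 ≤ 0.90
- ties excluded: F(x−1) ≥ 0.10 and F(x) ≤ 0.90

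The pass probability is the sum of P(X = x)·P(Y = y) over passing pairs.

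| True CR, Stage 3 vs 4 | Inclusive | Mid-percentile | Ties excluded |
|---|---|---|---|
| 60% vs 40% | 61% | 53% | 34% |
| 70% vs 50% | 60% | 53% | 33% |
| 80% vs 60% | 60% | 51% | 30% |
| 60% vs 30% | 37% | 27% | 16% |
| 60% vs 60% | 88% | 82% | 63% |

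The last row shows the opposite error: with identical 60% rates the inclusive check blocks pooling 100 − 88 = 12% of the time. If mITT leaves 10 vs 37, a 20-point loss passes 68–69% (inclusive) and 56–59% (mid-percentile).

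**One outcome.** With 8/13 (62%) vs 15/37 (41%), T = 23, F(7) = 0.837 and F(8) = 0.949. Since 0.837 < 0.90 it passes inclusively. The mid-percentile is (0.837 + 0.949)/2 = 0.893, which also passes. With ties excluded it fails. So an observed 21-point gap can be classed as consistent with one distribution.

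**Adding the duration test.** This was simulated (3,000 trials, 1,000 permutations each) assuming difference in median duration as the statistic, uncensored exponential durations, and both tests required. With CR 20 points lower and equal durations, the joint pass rate is about 49% at each reference rate. With a relapse hazard 1.5 times higher in Stage 4 it is 39–45%.

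**What the cohorts can resolve.** At a common rate of 60%, SE = √[0.6 × 0.4 × (1/13 + 1/37)] = 0.158, so the 95% half-width is 1.96 × 0.158 = 31 points. Adding the 16 earlier patients (13 + 16 = 29) gives SE 0.122 and about 24 points.

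**Follow-up at the 13 March 2020 cut-off.** Time since enrollment is about 36–41 months in Stage 3 (enrolled 26 October 2016 to 17 March 2017) and about 14–36 months in first-line Stage 4 (after 17 March 2017 to 7 January 2019).

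**The case against.** Several replies have force.

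- **The rule does not usually pass.** A reader might infer from the 61% that a 20-point loss normally slips through. That needs the inclusive tie reading and the CR test alone. Mid-percentile gives about half, exclusion of ties about a third, and a joint requirement about 49% at best. At a 30-point loss every reading fails more often than it passes. This stands.
- **Overlap of the 90% intervals is not a stated criterion.** A reader might compute how often the intervals overlap and treat that as the plan's rule. The SAP asks only for a comparison of coverage, so overlap frequencies do not describe its decision. This stands.
- **Nothing is hidden.** A reader might infer that pooling masks a poor lyophilized result. Table 3-1 has separate Stage 3 and Stage 4 columns for every listed endpoint, SAP 4.3 repeats reporting by stage, and SAP 4.3.1 gives 95% intervals for response rates. At 60% vs 40% the expected pooled rate is (13 × 0.6 + 37 × 0.4)/50 = 45%, 5 points above Stage 4 alone. This stands and limits the harm.
- **No confirmatory claim depends on the gate.** The only formal test is Stage 3 CR against 10%, secondary analyses are descriptive (SAP 3.8.2), and the pooling wording is permissive. It is fair that the SAP does not claim equivalence, but it does assign the result a supporting role for formulation similarity.
- **The duration test is not shown to be invalid.** SAP 4.3.2 defines censoring and uses Kaplan-Meier for estimation. Unequal follow-up upsets exchangeability only if the permutation statistic ignores censoring, and 3.5.1 does not say which statistic is used. The defect is missing specification.
- **Stages 1–2 are not a neutral comparator.** Those data were used to decide that CRc counts toward CR and CRi does not (SAP 1.1.3). That confines them to a sensitivity analysis.

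**Conclusion.** The concern holds in a limited form. Reading non-rejection at a two-sided 20% level as support for similarity, with no margin and about 13 vs 37 patients, is not a sound inference. Under an assumed 60% vs 40%, the CR check misses the loss 61%, 53% or 34% of the time across the three tie readings. The spread is itself a specification gap. Requiring the duration test too lowers the figure to about 49% at best, under the simulated statistic and equal durations, and the SAP does not say both must pass.

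The consequence is an unsupported similarity statement and a pooled estimate conditional on a test. The documents do not support the stronger conclusions that the rule passes in most trials with such a loss, that the lyophilized result would be concealed, or that the duration test is wrong as planned.

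The figures rest on enrolled and treated counts and on an assumed 20-point difference. Reducing Stage 3 to 10 raises the inclusive and mid-percentile pass rates.

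**What to change.** In SAP 3.5.1:

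1. Stop using the 10th–90th percentile rule and the 90% interval comparison, both as evidence of similarity and as a gate for pooling.
2. Keep the planned Stage 3 and Stage 4 summaries, and show the pooled estimate as descriptive only, whatever the comparison shows.
3. Add the Stage 4 (lyophilized) minus Stage 3 (frozen) difference in CR rate with a 95% exact or score interval, expected at about ±31 points.
4. Add a sensitivity version that includes the first-line 12 µg/kg/day frozen patients of Stages 1–2, at about ±24 points. Note that those data informed the CR + CRc definition and that 16 is an interim count.
5. Compare duration of CR by a censoring-aware method: Kaplan-Meier with log-rank, or truncation at a common follow-up.
6. State that a non-significant difference is inconclusive and is not evidence of similarity.

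The cost is SAP rewording and one extra table, with no new data. The sponsor gives up a favorable similarity statement. The change makes the uncertainty visible but does not remove it: even the larger comparison could not exclude a 20-point loss if the observed rates were equal at 60%.
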